6.4. Follow-up Period for Survival and Initiation of Anticancer Therapy

Post-treatment survival time and any subsequent anticancer therapy information status will be monitored approximately every 12 weeks (+/-3 weeks) from EOT Visit or more frequently as needed, until death, withdrawal of consent, or the study closes, whichever is earliest. This evaluation may be by record review and/or telephone contact.

6.5. Pharmacokinetic Study

A PK study of rapamycin will be performed with limited PK sampling on all patients in this phase 2 study. Blood samples will be obtained during Cycle 1 Day 1 (C1D1) immediately predose (before infusion), 0.5 hr (immediately before termination of infusion), 1 hr, 2 hrs, and 4 hrs; during Cycle 1 Day 8 (C1D8) immediately predose (before infusion), 0.5 hr (immediately before termination of infusion), 1 hr, 2 hrs, and 4 hrs, and on Cycle 2 Day 1 (C2D1) immediately predose (before infusion). All samples should be collected within a window of +/- 10 minutes. Note that T = 0 is defined as the start of infusion, ie, all sample collection times are relative to the start of infusion. The sample at the end of the infusion (0.5 hour) is collected immediately before the infusion is stopped. If the duration of infusion is changed, the sample should be collected immediately before termination of the infusion.

Whole-blood samples will be collected in EDTA tubes for determination of rapamycin in a central laboratory.

Time Recording:

- The exact clock time for the start and end of infusion must be recorded.
- The exact clock time of each collection must be recorded.

6.6. Biomarker Development

The key objective of the tumor molecular profiling is to identify specific markers that are predictive of response to ABI-009. The key objective of the biomarker blood sampling is to investigate whether blood sampling can serve as a “liquid biopsy” to monitor disease progression.

- **Blood samples** will be obtained for cell-free plasma DNA collection (pretreatment, Cycle 4/Day 1, and post-treatment) for all patients:
 - **Molecular analysis of cell-free plasma DNA assay** using next-generation sequencing to assess the prevalence of mutations identified in the primary tumor sample over time as a measure of response to therapy.
- **Tumor biopsy mutation analysis to assess resistance mechanisms.** Pre-treatment tumors (archival or fresh tissue biopsies) are required for all patients on this study to confirm diagnosis. This sample will also be used for baseline mutational analysis. In addition, an optional tumor biopsy will be collected for patients who provide additional consent at the end of treatment and/or if a patient experiences progression while on study.

Tumor biopsies are to be collected and pharmacodynamic changes analyzed to determine the effect of the drug on target(s) in the tumor as well as to potentially analyze molecular mechanisms associated with acquired resistance.

- **Exome sequencing** using the Oncopanel test (BWH Pathology Department, CLIA certified) of approximately 300 genes will be performed to assess mutations in all the known mTOR pathway genes, including but not limited to PIK3CA, TSC1, TSC2, AKT, PTEN, MTOR, and RHEB. Rationale: TSC1 and TSC2 mutations are known to occur at high frequency in PEComa.
 - Evaluate correlation to clinical response to the therapy.
 - Test the correlation between biopsy and circulating DNA.
- FISH (fluorescence in-situ hybridization) analysis of translocations in TFE3. TFE3 translocations are known to occur at low frequency in PEComa. These studies will be performed centrally in a laboratory that is CLIA certified.
- **Immunohistochemistry** on relevant pathway markers, including but not limited to:
 - phosphoproteins p-AKT, p-S6, p-4EBP1, SPARC
 - proliferation marker, such as Ki-67
 - apoptosis marker, such as PARP
 - Post-treatment (progression) samples will be analyzed by similar exome sequencing as above, to search for causes of resistance, including secondary mutations and genomic amplification or deletion events.

7. DESCRIPTION OF STUDY TREATMENTS

7.1. ABI-009 Dosage, Administration, and Schedule

Treatment cycles are 21 days in duration and patients are treated until disease progression or unacceptable toxicities. Patients will receive ABI-009 100 mg/m² (IV infusion over 30 minutes, +/- 10 min) weekly for 2 weeks followed by a week of rest (2/3 weekly schedule). The schedule 2 weeks out of a 3 weekly schedule will allow the patient to have 1 week rest, when most of the toxicities occur, based on experience in the phase 1 study of ABI-009 (Protocol CA401) [38]. In terms of dose intensity within 6 months (24 weeks), the 2 out of 3 weekly schedule will consist of 16 administrations compared to 18 administrations with the prior 3 out of 4 weekly schedule. This reflects a global dose intensity reduction of 11% when comparing the 2 schedules. Two dose reduction levels are allowed: 75 mg/m² and 56 mg/m². A physician must be available at the time of administration of IP on dosing days that correspond to study visits. Supportive care per the institution's normal standard of care including concomitant medications can be provided at the investigator's discretion.

7.2. Dose Modification and Stopping Rules

7.2.1. Dosage Adjustments, Delays, Rules for Withholding or Restarting, Permanent Discontinuation

If, treatment cannot be administered on the planned visit date, ABI-009 may be administered +/- 2 days from the scheduled date. Prior to ABI-009 administration on Day 1 of each cycle, patients must meet the following hematological requirements:

- ANC $\geq 1.5 \times 10^9/L$
- Platelet count $\geq 100 \times 10^9/L$
- Hemoglobin $\geq 9 \text{ g/dL}$

The treatment will be on hold up to 14 days until the patient has fulfilled these criteria.

Day 1 Dose Missed

If the dose held or missed was to be given on Day 1 of the next cycle, that next cycle will not be considered to start until the day the first dose is actually administered to the patient (ie, D1-D8-Rest, X-D1-D8-Rest, etc).

Day 8 Dose Is Missed

That week becomes the week of rest. Next dose (if counts and chemistries permit) becomes Day 1 of a new cycle (ie, D1-D8-Rest, D1-X, D1-D8-Rest, etc).

The maximum delay between a missed scheduled dose and the next one (whichever dose was missed) should not be longer than 14 days. Approval from the Medical Monitor is required to restart study treatment after ≥ 21 days of interruption.

Doses will be reduced for hematologic and other toxicities. Two levels of dose modifications are permitted according to the criteria below. Dose reductions will occur

sequentially (75 mg/m² and 56 mg/m²), there should be no direct reduction by two dose levels. If a toxicity requiring dose modification occurs following the second dose reduction of ABI-009, further treatment should be discontinued. Dose adjustments are to be made according to the system showing the greatest degree of toxicity. Toxicities will be graded using the NCI CTCAE Version 4.03.

Guidelines for dose modifications and interruptions for management of common toxicities associated with the study treatment(s) are provided in this section:

- General guidelines for clinically significant toxicities related to study treatment

And

- Specific guidelines for adverse events of special interest, which are events that have been observed with higher frequency or severity.

In the event of clinically significant AE in any part of the study, treatment may be withheld and supportive therapy administered as clinically indicated. If the toxicity or event is not grade 3/4 and resolves to baseline or grade 1 in less than or equal to 14 days of stopping therapy, then treatment may be restarted. Dose reduction of ABI-009 should be considered as clinically indicated.

If the toxicity does not resolve to at least grade 1 in less than 14 days, withdrawal from treatment with the IP is recommended. However, if the investigator and AADi Medical Monitor agree that further treatment would benefit the patient, treatment can continue with at least one dose level dose reduction, per [Table 4](#).

Table 4: Dose Level Reduction Guidelines

Dose level	ABI-009 Dose/Schedule
0	Initial Dose: 100 mg/m ²
-1 (first dose reduction)	25% reduction of initial dose of 100: 75 mg/m ²
-2 (second dose reduction)	25% reduction from 75 mg/m ² : 56 mg/m ²

If an AE resolves to grade 1 or baseline at the reduced dose level, and no additional toxicities are seen during the following cycle of study treatment at the reduced dose, the dose may be increased to the previous dose level.

Any patient meeting the criteria for Hy's Law case (i.e. severe drug-induced liver injury) will be considered a dose-limiting toxicity. A Hy's Law case is defined as: AST or ALT values of $\geq 3 \times$ ULN AND with serum total bilirubin level (TBL) of $> 2 \times$ ULN without signs of cholestasis and with no other clear alternative reason to explain the observed liver-related laboratory abnormalities.

ABI-009 dose modification guidelines are outlined in [Table 4](#) and [Table 5](#): for clinically significant toxicities that are deemed related. The dosing schedule is described in the Schedule of Assessments, [Table 2](#).

Table 5: Dose Modification Algorithms for Adverse Events Possibly Related to ABI-009

System/Organ	Adverse Event	CTCAE Grade v4.03	Dose modification Algorithm
Mucosa	Stomatitis, mucosal inflammation	Grade 2	Hold ABI-009 until resolution to Grade 1 or baseline and restart at the same dose for 1 st occurrence; for subsequent occurrences, drug will be restarted at a reduced dose; provide supportive care as clinically indicated.
		Grade ≥3	Hold ABI-009 until resolution to Grade 1 or baseline and restart at the same dose for 1 st occurrence for subsequent occurrences, drug will be restarted at a reduced dose; provide supportive care as clinically indicated.
Skin and Subcutaneous Tissue Disorders	Skin rash	Grade 2	Tolerable: Continue ABI 009 at full dose, monitor as clinically indicated
			Intolerable: Hold ABI-009 until resolution to Grade 1 or baseline and restart at the same dose for 1 st occurrence; for subsequent occurrences, drug will be restarted at a reduced dose; provide supportive care as clinically indicated.
		Grade ≥3	Hold ABI-009 until resolution to Grade 1 or baseline; for subsequent events, drug will be restarted at a reduced dose; provide supportive care as clinically indicated.
Gastrointestinal Disorders	Diarrhea despite optimal medication	Grade 2	Hold ABI-009 until resolution to Grade 1 or baseline and restart at the same dose for 1 st occurrences; for 2 nd and subsequent events, drug will be restarted at a reduced dose; provide supportive care as clinically indicated.
		Grade ≥3	Hold ABI-009 until resolution to Grade 1 or baseline; for subsequent events, drug will be restarted at a reduced dose; provide supportive care as clinically indicated.
Metabolic disorders	Hyperlipemia (cholesterol, triglycerides)	Grade 3	If this is persistent for 2 months, reduce by 1 dose level at start of next cycle

		Grade 4	If this is persistent for 1 month, reduce by 1 dose level at start of next cycle
	Hyperglycemia	Grades 1 and 2	Start at home 2x/day glucose monitoring; initiate medical management
		Grade 3	Initiate medical management ; If recurrent post ABI-009 despite adequate medical management, reduce by 1 dose level
		Grade 4	Initiate medical management, hold ABI-009 until grade 2 or less, restart 1 dose level lower
Hematologic toxicity	Thrombocytopenia, Neutropenia, Anemia	Grade 2	ABI-009 can resume once meeting the following hematological requirements: ANC $> 1.5 \times 10^9/L$, platelets $> 100 \times 10^9/L$ and hemoglobin $\geq 9 \text{ g/dL}$
		Grade ≥ 3	Hold ABI-009 immediately for the remainder of that cycle. Repeat blood collection within 3 days. ABI-009 can resume once meeting following requirements: absolute ANC $> 1.5 \times 10^9/L$, platelet count $> 100 \times 10^9/L$ and hemoglobin $\geq 9 \text{ g/dL}$. For 2 nd and subsequent events, drug will be restarted at a reduced dose; G-CSF may be given as deemed indicated.
Respiratory events	Pneumonitis, bronchiolitis obliterans, and/or organizing pneumonia	Grade 2	Hold ABI-009 immediately for up to 3 weeks until resolved to \leq grade 1, then reduce by 1 dose level. If it is still a Grade 2 after 3 weeks, discontinue treatment. If $>$ Grade 2 recurs after resuming ABI-009 at a reduced dose level, discontinue treatment
		Grade ≥ 3	Permanently remove patient from protocol treatment

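### As printed, the pneumonitis recurrence stop in Table 5 covers only grade 3 or higher, which the next row already removes, so a quickly resolving grade 2 recurrence at 75 mg/m² may be restarted at 56 mg/m²

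*Combined protocol and SAP*

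**What the plan says.** Table 5 in Section 7.2.1 has two rows for pneumonitis, bronchiolitis obliterans and organizing pneumonia.

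- **Grade 2 row, first sentence.** "Hold ABI-009 immediately for up to 3 weeks until resolved to" grade 1 or lower, then restart one dose level down.
- **Grade 2 row, second sentence.** "If it is still a Grade 2 after 3 weeks, discontinue treatment".
- **Grade 2 row, third sentence.** "Grade 2 recurs after resuming ABI-009 at a reduced dose level, discontinue treatment". A greater-than sign stands immediately before the quoted words.
- **Grade 3 or higher row.** "Permanently remove patient from protocol treatment".

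General rules in the text of Section 7.2.1 also apply.

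- The dose steps are 100, 75 and 56 mg/m², taken one at a time. "If a toxicity requiring dose modification occurs following the second dose reduction of ABI-009, further treatment should be discontinued".
- An event that is not grade 3 or 4 and settles to grade 1 or baseline within 14 days may be followed by a restart.
- "If the toxicity does not resolve to at least grade 1 in less than 14 days, withdrawal from treatment with the IP is recommended", although the investigator and the medical monitor can agree to continue at a dose at least one level lower.
- The gap between a missed dose and the next one "should not be longer than 14 days". Restarting after an interruption of 21 days or more needs the medical monitor's approval.

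Section 11.1 leaves removal from treatment for an adverse event to the investigator's judgment.

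**The concern.** A recurrence rule placed in the grade 2 row should settle what happens when grade 2 pneumonitis returns on a reduced dose. As printed it does not. Above grade 2 means grade 3 or higher, and the row below already takes those patients off treatment at any occurrence. The grade that the rule was needed for is left out.

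The wording and placement suggest that grade 2 was meant to be covered. A patient whose first episode was grade 3 or higher has already left treatment, so within this row it is a grade 2 event that can recur. Respiratory events are also the only group in Table 5 with a discontinuation rule for recurrence. Repeat stomatitis, rash, diarrhea and hematologic events lead to a restart at a reduced dose.

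What is at stake is patient safety. Section 1.2.1 describes pneumonitis with oral rapamycin and rapalogs as sometimes fatal. A site that follows the table literally may re-expose a patient who has already had two grade 2 episodes.

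**Working it through.** **Step 1: trace a recurrence at 75 mg/m².** The patient had a first grade 2 episode at 100 mg/m², recovered and restarted at 75 mg/m². The next level is 75 × 0.75 = 56.25, given in Table 4 as 56 mg/m².

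| Recurrence at 75 mg/m² | Printed recurrence stop | Other rules | Result as printed | Result if the stop read grade 2 or higher |
|---|---|---|---|---|
| Grade 3 or higher | Applies | Grade 3 or higher row removes permanently | Stop | Stop |
| Grade 2, unresolved after 3 weeks | Does not apply | Second sentence of the grade 2 row | Stop | Stop |
| Grade 2, resolved between 14 days and 3 weeks | Does not apply | Withdrawal recommended unless investigator and medical monitor agree; 14-day limit on delay | Restart at 56 mg/m² only by agreement | Stop |
| Grade 2, resolved in under 14 days | Does not apply | None requires a stop | Restart at 56 mg/m² permitted | Stop |

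In the first line the patient stops with or without the recurrence sentence. In the other three lines the sentence is not triggered. It therefore never changes an outcome. A grade 2 recurrence at 56 mg/m² stops under the two-reduction limit on either reading.

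**Step 2: expected number of patients.** Section 1.2.1 gives pneumonitis rates of 8% overall and 3% at grade 3 for oral rapamycin and currently available rapalogs. Assume that these rates apply to ABI-009, and take 30 treated patients.

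- Expected pneumonitis other than grade 3: (0.08 − 0.03) × 30 = 1.5 patients.
- Only some of these would be grade 2, resolve, be restarted and then recur at grade 2. The documents give none of these shares. Assumed ranges: 50–100% grade 2, 50–100% resolved and restarted, 20–50% recurring at grade 2.
- Low end: 0.05 × 0.5 × 0.5 × 0.2 = 0.0025 per patient. Expected number 0.0025 × 30 = 0.075. Chance of at least one case 1 − (1 − 0.0025)^30 = 0.072.
- High end: 0.05 × 1 × 1 × 0.5 = 0.025 per patient. Expected number 0.025 × 30 = 0.75. Chance of at least one case 1 − (1 − 0.025)^30 = 0.532.

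**Step 3: the drug's own phase 1 data.** Table 1 (Section 1.2.2.2) lists treatment-related events in at least 10% of 26 patients. Since 0.10 × 26 = 2.6, a listed event needs 3 or more patients. Pneumonitis is not listed, so at most 2 of 26 (7.7%) had it as a treatment-related event under that term. This neither confirms nor excludes the class rate. Exclusion criterion 11 (Section 4.3) also keeps out patients with a history of pneumonitis, which may lower the rate here.

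**Step 4: how far the sign can be trusted.** The point rests on one character in text read from PDF.

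- For the sign being as printed: a less-than-or-equal sign survives in the same cell and a greater-than-or-equal sign in the next row.
- Against: the Table 5 hematologic rows print a plain greater-than sign for ANC and platelets beside greater-than-or-equal for hemoglobin, while the Day 1 requirements in Section 7.2.1 print greater-than-or-equal for all three. Section 6.3 prints a plus sign on the 7-day visit window where Section 3.3 and Table 2 print plus-minus.

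These mismatches may be reading losses or inconsistencies in the source. The documents cannot settle which.

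**The case against.** The strongest objection is that the defect may not exist. An underlined greater-than sign can lose its underline when a PDF is read, and the hematologic rows show that an intact neighboring sign proves little. The word for recurrence, in a grade 2 row, itself points to greater-than-or-equal. This stands as a reason to check the source first. It does not change what the available text says.

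A second objection is that, if the strict sign was intended, a second reduction after a resolved grade 2 event fits the two-step dose scheme. That would be a defensible policy, but the recurrence sentence would then have no function.

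A third is that safeguards remain: investigator judgment (Section 11.1), physician decision as a reason to stop (Section 12.1), the 14-day rules, medical monitor approval after 21 days, and the external DMC safety review (Section 10.3). They limit the consequence. None requires a stop for the quickly resolving case.

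Three stronger readings are tempting and are not supported.

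- **Repeated cycling between dose levels.** A reader might infer this because, after a clean cycle, "the dose may be increased to the previous dose level". That provision concerns an event that resolves at the reduced dose. The pneumonitis row requires resolution during the hold, before the reduced dose begins, so the inference is doubtful and is not relied on here.
- **A maximum of 1.5 patients.** The figure is an expected count under a borrowed rate, not a bound. Section 4.1 plans at least 30 evaluable patients, so more may be treated.
- **Mandatory re-exposure.** The text permits a restart; it does not compel one.

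**Conclusion.** On the text as printed, the concern holds. The recurrence stop has no effect, and a grade 2 recurrence at 75 mg/m² that resolves to grade 1 or lower in under 14 days may be restarted at 56 mg/m². The gap is confined to that path, plus slower episodes for which the investigator and medical monitor agree to continue.

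Severity is low. Under the assumed class rates and shares, the expected number affected is 0.075 to 0.75 per 30 treated patients, with a 7% to 53% chance of at least one case. These counts scale with the number treated. The shares are assumptions without support in the documents, and the class rate may not carry over to ABI-009. The definition, population and confidence interval of the primary ORR analysis (Section 10.5.2) are not touched.

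Confidence is medium, because everything depends on one sign that the PDF reading may have altered.

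**What to change.** Check the sign in the source file. If it already reads greater-than-or-equal, no change is needed. Otherwise, in the third sentence of the grade 2 respiratory row, delete the sign and write Grade 2 or higher, leaving the rest of the clause as it is. Any recurrence of grade 2 or above after a restart at a reduced dose would then end treatment.

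The change is one clause in Table 5, with no added visits, patients or analyses. Its clinical cost is that a patient with a second grade 2 episode, possibly a responder, loses a further restart at 56 mg/m². If the sponsor does want to allow that restart, the recurrence sentence should be removed and the second reduction stated openly.

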7.2.2. Hepatotoxicity Stopping Rules

Patients with abnormal hepatic laboratory values (ie, ALP, AST, ALT, total bilirubin TBL) and/or international normalized ratio (INR) and/or signs/symptoms of hepatitis may meet the criteria for withholding or permanent discontinuation of ABI-009 as specified in the Guidance for Industry Drug-Induced Liver Injury: Premarketing Clinical Evaluation, July 2009.

7.2.2.1. Criteria for Permanent Discontinuation of ABI-009 Due to Potential Hepatotoxicity

ABI-009 should be discontinued permanently and the patient should be followed for possible drug-induced liver injury (DILI), if **ALL** of the criteria below are met:

- TBL > 2x upper limit of normal (ULN) or INR > 1.5x
- AND increased AST or ALT from the relevant baseline value as specified below:

Baseline AST or ALT value	AST or ALT elevation
< ULN	≥ 3x ULN

- AND no other cause for the combination of the above laboratory abnormalities is immediately apparent; important alternative causes for elevated AST/ALT and/or TBL values include, but are not limited to:
 - Hepatobiliary tract disease
 - Viral hepatitis (eg, Hepatitis A/B/C/D/E, Epstein-Barr Virus, Cytomegalovirus, Herpes Simplex Virus, Varicella, Toxoplasmosis, and Parvovirus)
 - Right sided heart failure, hypotension or any cause of hypoxia to the liver causing ischemia.
 - Exposure to hepatotoxic agents/drugs or hepatotoxins, including herbal and dietary supplements, plants and mushrooms
 - Heritable disorders causing impaired glucuronidation (eg, Gilbert's Syndrome, Crigler-Najjar syndrome) and drugs that inhibit bilirubin glucuronidation (eg, indinavir, atazanavir)
 - Alpha-one antitrypsin deficiency
 - Alcoholic hepatitis
 - Autoimmune hepatitis
 - Wilson's disease and hemochromatosis
 - Nonalcoholic Fatty Liver Disease including Steatohepatitis (NASH)
 - Non-hepatic causes (eg, rhabdomylosis, hemolysis)

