4.2. Inclusion Criteria

A patient will be eligible for inclusion in this study only if all of the following criteria are met:

1. Patients must have a histologically confirmed diagnosis of malignant PEComa that is either metastatic or locally advanced and for which surgery is not a recommended option.
2. Patients must have available tumor block along with the corresponding pathology report (or approximately 30 unstained slides, with a minimum of 16 slides), and/or fresh biopsy to allow retrospective centralized confirmation of malignant PEComa and for mTOR pathway analysis and biomarker analysis.
3. Patients must have one or more measurable target lesions by CT scan or MRI. Measurable disease by RECIST v1.1.
4. Patients must not have been previously treated with an mTOR inhibitor.
5. Prior treatment (investigational or other), chemotherapy, radiotherapy, surgery, or other therapeutic agents (except mTOR inhibitors) is allowed, if completed after 5 half-lives or ≥ 28 days prior to enrollment, whichever is shorter.
6. Eligible patients, 18 years or older, with Eastern Cooperative Oncology Group (ECOG) performance status 0 or 1.

7. Patients must have the following blood chemistry levels at screening (obtained ≤ 14 days prior to enrollment (local laboratory):
 - a. total bilirubin $\leq 1.5 \times$ upper limit of normal (ULN) mg/dl
 - b. AST $\leq 2.5 \times$ ULN ($\leq 5 \times$ ULN if attributable to liver metastases)
 - c. serum creatinine $\leq 1.5 \times$ ULN
8. Adequate biological parameters as demonstrated by the following blood counts at screening (obtained ≤ 14 days prior to enrollment, local laboratory):
 - a. Absolute neutrophil count (ANC) $\geq 1.5 \times 10^9/L$;
 - b. Platelet count $\geq 100,000/mm^3$ ($100 \times 10^9/L$);
 - c. Hemoglobin ≥ 9 g/dL.
9. Serum triglyceride < 300 mg/dL; serum cholesterol < 350 mg/dL.
10. Male or non-pregnant and non-breast feeding female:
 - Females of child-bearing potential must agree to use effective contraception without interruption from 28 days prior to starting IP and while on study medication and have a negative serum pregnancy test (β -hCG) result at screening and agree to ongoing pregnancy testing during the course of the study, and after the end of study treatment. A second form of birth control is required even if she has had a tubal ligation.

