7.2.2.2. Criteria for Conditional Withholding of ABI-009 Due to Potential Hepatotoxicity

For patients who do not meet the criteria for permanent discontinuation of ABI-009 and have no underlying liver disease, and eligibility criteria requiring normal transaminases and TBL at baseline or patients with underlying liver disease and baseline abnormal transaminases, the following rules are recommended for withholding of ABI-009:

- Elevation of either AST or ALT according to the following schedule:

Baseline AST or ALT value	AST or ALT elevation
Any	> 8x ULN at any time
Any	> 5x ULN but < 8x ULN for ≥ 2 weeks
Any	> 5x ULN but < 8x ULN and unable to adhere to enhanced monitoring schedule
Any	≥ 3x ULN with clinical signs or symptoms that are consistent with hepatitis (such as right upper quadrant pain/tenderness, fever, nausea, vomiting, jaundice).

- OR: TBL > 3x ULN at any time
- OR: ALP > 8x ULN at any time

ABI-009 should be withheld pending investigation into alternative causes of DILI. Rechallenge may be considered if an alternative cause for impaired liver tests (ALT, AST, and ALP) and/or elevated TBL is discovered and the laboratory abnormalities resolve to normal or baseline.

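### The permanent-stop table in 7.2.2.1 has no row for AST or ALT at or above ULN at entry, so a raised enzyme cannot trigger the stop, and a band of asymptomatic rises triggers no liver rule

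*Combined protocol and SAP*

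**What the plan says.** **Permanent stop (7.2.2.1).** The drug should be stopped for good if all three criteria hold: bilirubin (TBL) > 2x ULN or INR > 1.5; "AND increased AST or ALT from the relevant baseline value as specified below"; and no other cause immediately apparent. The table has a single row: baseline < ULN, on-study value >= 3x ULN.

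**Eligibility (4.2, criterion 7).** AST may be up to 2.5x ULN, or 5x "ULN if attributable to liver metastases". TBL must be <= 1.5x ULN. ALT is not mentioned.

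**Withholding (7.2.2.2).** The scope includes "patients with underlying liver disease and baseline abnormal transaminases", and all four enzyme rows apply at any baseline. Withholding is recommended above 8x ULN; at 5-8x ULN for 2 weeks or more, or if enhanced monitoring is not possible; at >= 3x ULN with signs of hepatitis, including jaundice; at TBL > 3x ULN; or at ALP > 8x ULN. There is no INR trigger.

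**Hy's Law (7.2.1).** The definition is AST or ALT >= 3x ULN with TBL > 2x ULN, no cholestasis and no other clear reason. It has no baseline condition. The text says "severe drug-induced liver injury) will be considered a dose-limiting toxicity" and attaches no action to that label.

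**General adverse-event guidance (7.2.1).** "In the event of clinically significant AE in any part of the study, treatment may be withheld". For an event other than grade 3/4, the rule is that if it "resolves to baseline or grade 1 in less than or equal to 14 days of stopping therapy, then treatment may be restarted". If it does not resolve, "withdrawal from treatment with the IP is recommended"; treatment may go on only if the investigator and medical monitor agree, and at least one dose level lower.

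**Rechallenge (7.2.2.3).** Patient, investigator and medical monitor must all agree. Patients who meet the permanent-discontinuation criteria may never be rechallenged, but the section cited for those criteria is 7.2.1, not 7.2.2.1.

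**The concern.** The stop is keyed to baseline, yet the table defines only one kind of baseline. Eligible patients can have an enzyme above ULN at entry, and for that enzyme the second criterion cannot be met however high it rises. Entry TBL is capped at 1.5x ULN, so TBL above 2x ULN on study is a new rise whatever the enzyme baseline. The same on-study values, with no other cause, would end treatment for a patient whose enzyme was normal at entry. For a patient whose enzyme was raised at entry, they could leave treatment running or allow a restart. The values at issue largely match what the protocol itself calls severe drug-induced liver injury.

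This is a patient-safety matter. ORR, its confidence interval and the sample size do not depend on it.

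**Working it through.** The plan states no figure to reproduce. The check codes the rules and runs them over a grid.

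**Rules**, for one enzyme with baseline b and on-study value v, both in multiples of ULN:
- Stop (7.2.2.1): b < 1, v >= 3, TBL > 2 or INR > 1.5, no other cause.
- Withhold (7.2.2.2): v > 8; or 5 < v < 8 if lasting >= 2 weeks or not monitorable; or v >= 3 with hepatitis signs; or TBL > 3; or ALP > 8.
- Example extra row: b >= 1 and v >= max(3, 2b), giving thresholds 3, 4, 5, 6, 8 and 10x ULN for b = 1.5, 2, 2.5, 3, 4 and 5.

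**Grid:** v = 3, 4, 5, 6, 7.5, 9, counting only values above baseline. TBL is 2.5x ULN, with no symptoms, ALP not above 8x ULN, no cholestasis, no other cause, and the other enzyme below 3x ULN. Open means that neither the stop nor a withholding rule acts.

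| Baseline (x ULN) | Stop fires | Open if >= 2 weeks or not monitorable | Closed by example row | Open if brief and monitored | Closed by example row |
|---|---|---|---|---|---|
| 0.8 | all 6 | 0 | - | 0 | - |
| 1.5 | never | 3 | 3 | 5 | 5 |
| 2.0 | never | 3 | 2 | 5 | 4 |
| 2.5 | never | 3 | 1 | 5 | 3 |
| 3 | never | 2 | 0 | 4 | 2 |
| 4 | never | 1 | 0 | 3 | 0 |
| 5 | never | 0 | 0 | 2 | 0 |

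For baselines 1.5-2.5x, the open cells are 3, 4 and 5x ULN (9 cells), plus 6 and 7.5x when brief and monitored (15 in all). The example row closes 6 of 9 and 12 of 15. The three left open (2.0 to 3x, 2.5 to 3x, 2.5 to 4x) are rises of less than 2-fold. At 9x ULN withholding applies at every baseline, as it does whenever TBL exceeds 3x ULN or hepatitis signs are present.

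**INR route:** with TBL 1.0x ULN and INR 1.6, the same enzyme values stay open, and the Hy's Law label does not apply either.

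**What acts in the open cells:** Table 5 has no hepatic row. The Day 1 dosing requirements in 7.2.1 are haematological only. After a missed Day 8 dose the next is given "if counts and chemistries permit", with no liver threshold stated there. That leaves the general guidance and, after a hold, the unanimous-agreement rule.

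**How many patients:** Table 1 lists treatment-related events in >= 10% of 26 phase 1 patients. AST is listed (1 + 2 = 3/26 = 11.5%; 0/7 at 100 mg/m²). Bilirubin is not, so at most 2/26 = 7.7% had such an event (exact 95% CI for 2/26: 0.9-25.1%). Assume 10-30% of 30 patients, that is 3-9, enter with a raised enzyme:
- 3 x 2/26 = 0.23 and 9 x 2/26 = 0.69 patients.
- At the upper confidence limit, 3 x 0.2513 = 0.75 and 9 x 0.2513 = 2.26.

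Both ranges count every bilirubin event as qualifying, before requiring a coincident enzyme rise, no symptoms and no other cause. INR events are not counted.

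**The case against.** **Raised baselines are already handled.** Section 7.2.2.2 names these patients and applies at any baseline, so withholding them pending a work-up may be the intended design. This stands for most larger or symptomatic rises. It does not reach the open band, and 7.2.2.1 does not say that raised baselines are left to 7.2.2.2.

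**Hy's Law covers the gap.** The definition has no baseline condition, the heading of 7.2.1 includes permanent discontinuation, and 7.2.2.3 points to 7.2.1. Read literally, such cases might already be barred from rechallenge. But 7.2.1 states no liver criterion for permanent discontinuation and no action for a dose-limiting toxicity, so this is an ambiguity and not a rule.

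**A stronger reading fails.** A reader might infer that the stop is mandatory for normal baselines and that everything is at the site's discretion for raised ones. The documents do not support that. The stop itself is worded as what should be done. Continuing an event unresolved at 14 days needs the medical monitor's agreement and a dose reduction. Rechallenge needs unanimous agreement. These central checks also limit how far sites could diverge. They apply to an unresolved event or a restart, so they do not compel a hold in the first place.

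**Liver metastases.** AST of 2.5-5x ULN is admitted only when metastases explain it, so the no-other-cause criterion would often fail there whatever row is added. This stands, and the example row closes none of the 5 open cells at baselines 4-5x. It does not apply to AST between 1x and 2.5x ULN, or to ALT.

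**Not every open cell is the same signal.** A rise from 2.5x to 3x is not comparable with one from 0.8x to 3x. This also stands, and is why the threshold should be relative to baseline.

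**Conclusion.** The concern holds in limited form. The permanent stop cannot fire on an enzyme at or above ULN at entry. For asymptomatic rises to 3-5x ULN, or brief monitored rises to 5-8x, with TBL 2-3x ULN or INR > 1.5, no withholding rule applies either. It would be wrong to conclude that such patients have no liver protection.

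Probably fewer than one patient would be affected. That rests on the assumed 10-30% with raised enzymes and on phase 1 data at 45-150 mg/m², and patients with raised baselines may differ. The grid shows how the rules behave, not how often. Section 7.2.2 relies on an external guidance not available here. A table row lost in PDF reading cannot be excluded, although the four-row table in 7.2.2.2 came through intact.

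The wording should be corrected because the change is small and a wrong restart after liver injury could be serious. Confidence is medium.

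**What to change.** 1. Add a row to 7.2.2.1 for baseline >= ULN, with a baseline-relative threshold set by the clinical team. An example is at least 2x baseline and at least 3x ULN, with the TBL/INR and no-other-cause criteria unchanged. The multiplier is illustrative; the documents give none. At baselines of about 4-5x (thresholds 8-10x) the row mainly adds permanence and the rechallenge bar, since drug is already withheld above 8x ULN.
2. State in 7.2.1 that a Hy's Law case meeting the applicable 7.2.2.1 enzyme threshold requires permanent discontinuation.
3. Point the never-rechallenge sentence in 7.2.2.3 to 7.2.2.1.

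If raised baselines are meant to be handled only under 7.2.2.2, say so in 7.2.2.1 instead of adding the row.

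The cost is a wording amendment (one row, one sentence, one cross-reference) and possibly a few more permanent stops, including in patients who are benefiting.
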